3.1 Dose Escalation

The first cohort of the SAD will start with a sentinel group. The decision to continue dosing the remainder of Cohort 1 will occur after a minimum of 24 hours following sentinel group dosing and after the Sponsor, in conjunction with the Principal Investigator, has determined that adequate safety and tolerability have been demonstrated. It is not possible to stop dosing during an individual cohort of the SAD, except for the first cohort of SAD where dosing may be stopped following the sentinel cohort if any safety signal/concern arises, or, if the food effect is assessed by crossing over a single cohort, after the dosing of that cohort in the fasting state.

Dose Escalation Review

A review period will take place after the dosing of all subjects in each cohort in order evaluate and interpret all PK and safety data collected. The review of all pertinent blinded safety/tolerability data will include physical examinations, ECGs, vital signs, clinical laboratory tests, cardiac monitoring, and AEs or serious adverse events (SAEs) through approximately Day 14 (SAD) and Day 21 (MAD). Also, data from the current dose cohort and all previous cohorts will be considered.

The Sponsor and Investigator will determine if there are sufficient data available to make a dose escalation decision. Any AEs of Grade ≥2 toxicities (per Division of Microbiology and Infectious Disease [DMID] toxicity table; Appendix 3) must be considered in the decision to escalate to the next dose level. PK analysis will be completed on the active treatment subjects and will be blinded by subject.

As data from each cohort is informative for dose escalation decisions in subsequent cohorts, review of unblinded data will be conducted after completion of each cohort by 2 experienced individuals not directly involved in the study, one of whom must be a physician. Per protocol, the dose escalation meeting and decision require PK data through the morning of Day 8 and approximately 14 days of safety data, depending on

the turnaround time of the bioanalysis. Upon completion of the review, they will communicate to the study team modifications, if any, that should be implemented for subsequent cohorts. See unblinding procedures (Section 6.2.6).

Note: Although safety data for deciding on escalating to the next dose or cohort will be through approximately 14 days (SAD, Part 1) or 28 days (MAD, Part 2), subjects will continue to be monitored for safety up to 10 weeks or longer after the last dose. The duration of the follow-up period will be based on the analysis of interim PK data. For Part 1, available subjects from Cohorts 4 and 5, and all subjects in Cohort 6 will be asked to return bi-weekly (+/- 2 days) up to 10 weeks or longer postdose. Subjects will complete the same procedures as required for Day 28 at each visit. For Part 2, subjects will be discharged 1 week after the last dose and will be asked to return every 3 weeks for an additional follow-up period of 15 weeks or longer for safety and PK evaluation. Subjects will complete the same procedures as required for Day 21 at each visit.

Upon review of relevant data, the Sponsor, in conjunction with the Investigator, may decide to:

- 1. Escalate the dose as planned.
- 2. Evaluate an intermediate dose level prior to proceeding to the next planned dose level if concerns arise from PK and safety that do not warrant ceasing escalation.
- 3. Repeat a given dose level in a new cohort of subjects.
- 4. Increase the dose of the next cohort if the PK is lower than expected in the previous cohort.
- 5. Add a cohort if the PK is lower than expected after a cohort and there are no safety concerns.
- 6. Halt the study.

During the dose-escalation phase of this first clinical trial, escalation will be guided by emerging safety and PK data.

Dose escalation to the next cohort (i.e., dose level) will not take place until the Sponsor, in conjunction with the Principal Investigator and Dose Escalation Committee, has determined that adequate safety, tolerability and PK from the previous cohort has been demonstrated. The IRB will be notified, and the next cohort will start once IRB approval is received.

3.2 Stopping Rules for Cohorts for Participants Receiving Active Drug

If any of the cohort stopping rules are met, cohort dosing must be stopped to allow review of the data by the Sponsor and the Investigator. As with dose escalation review, the review of data here is also blinded except for review by the 2 experienced

individuals not directly involved in the study (see unblinding procedures; Section 6.2.6).

Rules for stopping dosing of a cohort include the following:

- a. One subject experiences one or more drug-related SAEs.
- b. Two or more subjects experience Grade 3 or 4 (per DMID) myalgia in combination with increase of CPK (at least 3 times the upper limit of the normal range [ULN] confirmed at 48 hours).
- c. Two or more subjects have a QTcF \geq 500 ms with an increase from baseline > 60 ms.
- d. Two or more subjects experience confirmed Grade 3 or 4 AEs (per DMID) in any one of the following laboratory parameters: alanine aminotransferase (ALT), aspartate aminotransferase (AST), alkaline phosphatase (ALP), amylase, or lipase.

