Note: PK sampling for deciding to escalate to the next dose will be through the morning of Day 15, i.e., will include the profile on Day 14, and the dose escalation meeting will take place around Day 28 when interim PK data is available from the bioanalysis lab. Therefore, the dose escalation meeting and decision will be based on PK through the morning of Day 15 and approximately 28 days of safety data, depending on the turnaround time of the bioanalysis.

Subjects will continue to be dosed up to 14 days and be monitored for safety at timepoints indicated in the schedule of assessments (Table 16). After the last dose, subjects will remain in the clinic for 7 additional days and will then enter an additional follow-up period of 15 weeks or longer, if indicated by interim PK analyses.

During each cohort, blood samples will be obtained before each dose of study drug, and at serial timepoints postdose on Days 1 and 14. Samples will be taken according to the schedule provided in Table 16, with the last sample being obtained on Day 126, or possibly later if a decision is made to extend monitoring. Plasma PK samples will be analyzed for TBAJ-876, M2, and M3 using validated analytical methods. Appropriate PK parameters will be calculated using non-compartmental methods. In addition, blood and urine will be collected for clinical laboratory evaluations.

For Cohorts 2 and 3, an additional ECG extraction will occur at 16 hours postdose on Day 1 and Day 14. For Cohort 3, all ECGs performed will be triplicate ECGs at each time point listed in Table 15, including the additional 16 hour postdose time point. The sampling and safety assessment schedule may be revised based on what is learned about PK from Part 1 of the study and it may be further revised based on evolving data in Part 2.

Female subjects will have blood collected for serum pregnancy testing. Females claiming postmenopausal status will have blood collected to measure FSH levels.

Subjects who withdraw from the study will not be replaced.

Part 3:

Part 3 is a single-dose design study with 3 planned dose groups each consisting of 10 subjects.

Subjects will be assigned to one of 3 groups and dose:

- Group 1: TBAJ-876 100 mg (1 x 100 mg tablet) under fasted conditions.
- Group 2: TBAJ-876 -100 mg (1 x 100 mg tablet) under fed conditions.
- Group 3: TBAJ-876 100 mg (4 x 25 mg tablets) under fasted conditions.

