For Cohort 7, a total of 124 mL (31 x 4 mL samples) will be collected from each subject for PK analysis. Approximately 78.5 mL of blood will be collected for the clinical laboratory evaluations and coagulation testing. The total volume of blood collected from each subject in Part 1 Cohort 7 will not exceed approximately 203 mL.

6.7.2 Part 2

A total of 212 mL (53 x 4 mL samples) will be collected from each subject for PK analysis. Approximately 110.6 mL of blood will be collected for the clinical laboratory evaluations and coagulation testing. The total volume of blood collected from each subject in Part 2 is planned not to exceed approximately 322.6 mL, although more may be collected if a decision is made to prolong PK monitoring.

Table 9 Total Volume of Blood to be Collected for Testing: Part 2

Reason for Collection	Number of Samples	Volume per Sample (mL)	Total Volume (mL)
Clinical labs at screening	1	12.5	12.5
Clinical labs during study (check-in, Days 7, 14, 21, 42, 63, 84, 105, and 126 (end-of-study)	9	8.5	76.5
Coagulation	8	2.7	21.6
Pharmacokinetic analysis (predose trough)	13	4.0	52.0
Pharmacokinetic analysis (postdose)	40	4.0	160.0
		Total	322.6

Additional PK samples may be collected at times to be determined based on the results from previous cohorts.

The Principal Investigator, in conjunction with the Sponsor, may collect additional blood if necessary, for repeat laboratory or safety evaluations including AE follow-up.

6.7.3 Part 3

A total of 128 mL (32 x 4ml samples) will be collected for PK Analysis. Approximately 91 mL of blood will be collected for the clinical laboratory evaluations and coagulation testing.

Table 10 Total Volume of Blood to be Collected for Testing: Part 3

Reason for Collection	Number of Samples	Volume per Sample (mL)	Total Volume (mL)
Clinical labs at screening	1	12.5	12.5
Clinical labs during study (check-in, 6 and 48 hours and Days 5, 7, 10, and 14 (end-of-study).	7	8.5	59.5
Coagulation	7	2.7	18.9
Pharmacokinetic analysis	32	4.0	128.0
		Total	218.9

The Principal Investigator, in conjunction with the Sponsor, may collect additional blood if necessary, for repeat laboratory or safety evaluations including AE follow-up.

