7.5 Follow up of Adverse Events

All AEs will be followed until:

- Satisfactory clinical resolution or stabilization; or
- End of the follow-up period; and
- All queries on these AEs have been resolved.

Certain long-term AEs cannot be followed until resolution within the setting of this protocol. In these cases, follow-up will be the responsibility of the treating physician. However, this will have to be agreed upon with the Sponsor Medical Monitor.

The investigator is obligated to perform or arrange for the conduct of supplemental measurements and/or evaluations as medically indicated or as requested by Sponsor or representative to elucidate the nature and/or causality of the AE or SAE as fully as possible. This may include additional laboratory tests or investigations, histopathological examinations, or consultation with other health care professionals. Investigator should contact Sponsor/designee to discuss appropriate medical follow-up if consultation required.

If a participant dies during participation in the trial or during a recognized follow-up period, the investigator will provide Sponsor/representative with a copy of any post-mortem findings including histopathology.

New or updated information on an SAE will be recorded in the originally completed CRF and submitted to Sponsor within 24 hours of the information becoming known per SAE reporting guidelines.

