7.7 Clinical Laboratory Adverse Events

Changes in the results of the Clinical Laboratory assessment results which the Investigator feels are clinically significant will be reported as AEs. It is the Investigators' responsibility to review the results of all laboratory tests as they become available. This review must be documented by the Investigators' dated signature on the laboratory report. For each abnormal laboratory test result, the Investigator needs to ascertain and document if this is a clinically significant change from baseline for that individual participant. This determination, however, does not necessarily need to be made the first time an abnormal value is observed. The Investigator may repeat the laboratory test or request additional tests to verify the results of the original laboratory tests. All laboratory changes greater than or equal to Grade 2 must be reported as an AE regardless of clinical significance.

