- i. Subjects will be followed up for safety and PK during follow-up at the following timepoints: **Dose Level 1**: PK samples to be collected at pre-dose, 0.5, 1, 2, 3, 4, 5, 6, 8, 10, 12, 16, 20, 24, 28, 32, 36, 40, 44, 48, 54, 60, 66, 72, 80, 88, 96, 120, 144, and 168 hours after dosing, then on Days 10, 14, 17, 21 and 28. **Other Dose Level Cohorts:** scheduling of PK sample collection will be based on the PK data collected from previous cohorts and could involve a different sampling schedule and require subjects return to the clinic for up to 10 weeks or longer after dosing.
- j. Continuous 12-lead Holter recording (cardiac telemetry) will begin 1 hour before and end 24 hours after dosing.
- k. ECGs on Day 1 will be extracted from a continuous 12 lead Holter recording at discrete timepoints as noted in above flow chart and will be extracted at the same time as vital sign measurements. If a subject experiences a post-dosing QTcF >500 msec or a change-from-baseline QTcF >60 msec, after repeat testing, additional ECGs should be recorded until normalization or return to baseline.
 NOTE: when ECG extractions coincide with safety ECGs, vital sign assessments, and/or blood draws, then procedures should be carried out in said order.

Table 16 Schedule of Assessments and Procedures, Part 2 MAD

PART 2	SCREEN	CHECK- IN ^a	СО	NFINEME	NT ^a		FOLLOW	/-UP	EARLY WITHDRAWAL
DAY	-28 to -2	-1	1 to 20	7, 14	21	42	63, 84, 105, 126	133	
EVENT									
Informed consent	X								
Check-in questions		X							
Medical history	X								
Height, weight	X								
HIV/ Hepatitis B, C	X								
Serum pregnancy test ^b	X	X							
FSH ^b	X								
Urine pregnancy ^c							X		X
Urine drug/alcohol/ cotinine screen	X	X							
Safety Labs hematology, chemistry, urinalysis) ^d	X	X		X	X	X	X		X
Coagulation	X	X		X	X	X	X		X
Physical exam	X	X		X	X	X	X		X
Heart murmur ^e	X	X	X	X	X	X	X		X
Vital signs (blood pressure, pulse, temperature, respiration rate, and pulse oximetry) ^f	X	X	X ^f	X	X	X	X		X
Concomitant medication review	X	X	X	X	X	X	X		X
Adverse events ^g		X	X	X	X	X	X	X	X
Breath strip applicationh			Xi	X					
Dose ⁱ			Xi	X					
12-lead safety ECGs ^j	X	X	X^{j}		X	X	X		X
Plasma for pre-dose trough PK ^k			X ^k	X					
Plasma for Post-dose PK ¹			X ^l	X	X	X	X		

PART 2	SCREEN	CHECK- IN ^a	СО	NFINEME	NT ^a		FOLLOW	EARLY WITHDRAWAL	
DAY	-28 to -2	-1	1 to 20	7, 14	21	42	63, 84, 105, 126	133	
EVENT									
Cardiac telemetry; 12-lead Holter monitoring ^m			X ^m	X ^m					

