- f. Vital signs (blood pressure, pule rate, temperature, respiration rate, and pulse oximetry) will measured at screening and check-in (Day -1). Vital sign measurements will be taken within 90 minutes prior to dosing and within 15 minutes of the defined time points at study hours 0, 1, 6, and 12 on Days 1 and 14. Furthermore, vital signs will also be taken once daily on Day 2 through Day 14 (6 hours after dosing) and once daily on Days 15-21 and Days 42, 63, 84, 105, and 126 and at early withdrawal (to be done within 15 minutes before review of medication and collection of adverse experiences). Both blood pressure and heart rate will be captured simultaneously. Blood pressure and heart rate will be measured after subjects are in a seated position for 2 minutes and then again after standing for 1 minute, except when they are supine or semi-reclined because of study procedures and/or adverse events, or as deemed necessary by the Investigator.
- g. AEs will be monitored from the time of signing the informed consent throughout the study via safety assessments, observation and participant reporting. Specific AE questions will be posed daily throughout the study until Day 21 and on all follow-up visits including a phone call on Day 133.
- h. TBAJ-876 or Placebo to TBAJ-876 Oral Suspension will be administered orally followed by 240 mL of water. Listerine® strips will be used as a blinding agent. A strip will be added to the subject's tongue before and after each dose.

Global Alliance for TB Drug Development

CONFIDENTIAL

- Dosing will only occur on Days 1-14.
- j. 12-lead safety ECGs will be printed and reviewed on-site by the Principal Investigator or designee. Triplicate ECGs will be completed at screening, Day -1, and on Day 15 or upon early withdrawal. All other time points will be single ECG readings. ECGs may be done within 2 hours prior to time of dosing and at 6 hours after dosing on Days 1, 2, 3, 8, 12, 14, and on Days 21, 42, 63, 84, 105, and 126. The predose ECG will be completed within 1 hour prior to the predose blood draw. If a participant experiences a postdose QTcF >500 ms or a change-from-baseline QTcF >60 ms, after repeat testing, additional ECGs should be recorded until normalization or return to baseline. All ECGs in Cohort 3 will be triplicate at each time point. In addition, subjects in Cohort 3 will have triplicate ECGs at 16 hours postdose on Day 1 and Day 14.
- k. Predose trough plasma samples will be drawn daily Days 1 through 14.

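### In Part 2, Day 7 is the only scheduled chemistry draw on which stopping rule d can spare more than the last dose; a Day 10 panel would add a second chance at little cost

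*Protocol*

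**What the plan says.** Protocol section 3.2 requires cohort dosing to stop for review if any listed rule is met. Rule d is the only one defined on laboratory values alone: "Two or more subjects experience confirmed Grade 3 or 4 AEs (per DMID) in any one of the following laboratory parameters", namely ALT, AST, ALP, amylase or lipase. It gives no confirmation interval; rule b uses 48 hours for CPK.

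Protocol Table 9 (section 6.7.2) lists the Part 2 draws as "Clinical labs during study (check-in, Days 7, 14, 21, 42, 63, 84, 105, and 126 (end-of-study". Table 16 (section 13) agrees: the row "Safety Labs hematology, chemistry, urinalysis" is blank in the Days 1 to 20 column and marked in the Days 7, 14 column. Its footnotes add that "Dosing will only occur on Days 1-14" and that "Predose trough plasma samples will be drawn daily Days 1 through 14".

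Parts 1 and 3 give one dose and schedule safety labs at 6 and 48 hours and on Days 5, 7, 10 and 14 (footnote e of Tables 15 and 17).

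Other provisions bear on the point. Section 7.7 states: "All laboratory changes greater than or equal to Grade 2 must be reported as an AE regardless of clinical significance". Section 7.5 states: "The investigator is obligated to perform or arrange for the conduct of supplemental measurements and/or evaluations as medically indicated". Section 6.7 lets the investigator, with the sponsor, take extra blood for repeat or safety tests. Section 3 (Part 2) states: "The sampling and safety assessment schedule may be revised based on what is learned about PK from Part 1 of the study".

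**The concern.** A rule that stops dosing can help only if results arrive while doses remain. With draws on Days 7 and 14 and dosing ending on Day 14, rule d has one scheduled result that leaves more than one dose to withhold.

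Protocol section 1.6 names liver and pancreatic effects as risks to be followed by chemistry biomarkers. It also reports that the lipase and amylase rises seen in Part 1 caused no symptoms, so symptoms may not prompt a for-cause draw. Section 1.7 says daily AUC was predicted to increase through 14 days of dosing. A rise that starts after Day 7 without symptoms would therefore have no planned look until dosing is ending, and subjects could receive a few doses that an earlier result would have spared.

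**Working it through.** **1. The plan's own count.** Check-in plus Days 7, 14, 21, 42, 63, 84, 105 and 126 is 9 draws; 9 x 8.5 = 76.5 mL. The Table 9 total is 12.5 + 76.5 + 21.6 + 52.0 + 160.0 = 322.6 mL. Both figures reproduce.

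**2. Doses spared.** Let the lag be the days from the draw to a confirmed result in hand before that day's dose. Doses spared = max(0, 14 - (draw day + lag) + 1). The documents give no turnaround time, so the lag is an assumption. The count also assumes that a cohort starts on one day.

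| Draw | lag 0 | 1 | 2 | 3 | 4 | 5 |
|---|---|---|---|---|---|---|
| Day 7 | 8 | 7 | 6 | 5 | 4 | 3 |
| Day 10 | 5 | 4 | 3 | 2 | 1 | 0 |
| Day 14 | 1 | 0 | 0 | 0 | 0 | 0 |

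**3. How much exposure rises after Day 7.** The footnotes to Tables 1-4 (Protocol section 1.4) predict AUC0-24h, in µg·hr/mL, for 25 mg daily on Day 28 (parent 2.1, M3 1.3) and after a single 400 mg dose (parent 10.4, M3 2.08). Assume dose linearity and ignore food. A single 25 mg dose then gives 10.4/16 = 0.65 and 2.08/16 = 0.13. The Day 28 multiples are:
- parent: 2.1/0.65 = 3.23
- M3: 1.3/0.13 = 10.0
- parent plus M3: 3.4/0.78 = 4.36

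Solve (1 - exp(-28k))/(1 - exp(-k)) for k at each multiple, then take (1 - exp(-7k))/(1 - exp(-14k)). Day 7 exposure is about 93% of Day 14 for parent, 86% for the sum and 67% for M3. For 200 mg daily, the single-dose equivalent is 200 x 3.23 = 646 mg (parent) and 200 x 4.36 = 872 mg (sum). These are Day 28 multiples, so Day 14 values would be slightly lower.

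**4. Chance of seeing two or more cases.** No event rate is given, so the rates are assumptions. X ~ Binomial(9, p·f), with onset uniform over Days 1-13: f = 6/13 at Day 7 and 9/13 at Day 10. To allow for Grade 2 follow-up, assume half of the Day 7-9 onsets are already caught without the new panel (f = 7.5/13).

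| p | Day 7 only | with follow-up | with Day 10 panel | gain over follow-up |
|---|---|---|---|---|
| 5% | 1.7% | 2.6% | 3.7% | 1 point |
| 10% | 6.2% | 9.1% | 12.5% | 3 points |
| 20% | 19.9% | 27.9% | 36.0% | 8 points |
| 30% | 36.0% | 47.9% | 58.7% | 11 points |

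Rule d needs both cases in one parameter. Splitting p = 5% evenly over five gives 1 - (1 - P(X≥2; 9, 0.01·f))^5, which rises from 0.4% at Day 7 to 0.8% at Day 10.

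Which rates are plausible? Section 1.6 reports no severe AEs in 47 single-dose subjects (blinded data, placebo included). The one-sided 95% upper bound is 1 - 0.05^(1/47) = 6%, or about 8% for 35-36 active subjects. The low rates are the better guide unless repeat dosing raises them.

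**5. False alarms.** At an assumed background Grade 3-4 rate of 0.5%, 1% or 2% per parameter per draw, P(X≥2) in 9 subjects is 0.09%, 0.34% or 1.31%. For any of five independent parameters it is 0.4%, 1.7% or 6.4%, before confirmation.

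**6. Blood.** 322.6 + 8.5 = 331.1 mL at most; 8.5/322.6 = 2.6%.

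**The case against.** The case for leaving the plan alone is substantial.

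- **It is a choice, not an error.** Tables 9 and 16 agree with each other and with rule d, and nothing in the documents requires a second mid-course panel. This stands.
- **Safeguards exist.** A Day 7 value of Grade 2 or above is already an AE with follow-up, AE questions are asked daily, subjects can be withdrawn (section 8.4) and the investigator can terminate the study (section 8.5). These narrow the gap. They do not plan a look for a subject whose Day 7 panel was below Grade 2 and who has no symptoms. The unblinded review (section 3.1) comes after a cohort is complete.
- **The human data are reassuring.** MAD Cohort 1 at 25 mg showed no hepatic or gastrointestinal toxicity (section 1.7). The enzyme rises listed in section 1.6 were in the 10 and 50 mg cohorts and resolved. This supports the low event rates and hence a small gain.
- **The benefit depends on turnaround.** Beyond a 3-day lag, a Day 10 draw spares one dose or none.
- **It may be moot.** The SAP's table titles give Cohort 3 as 200 mg, although SAP section 6.3 still shows the dose as TBD. The documents do not say whether Cohort 3 has been dosed.

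A reader might infer something stronger on exposure. Taking the 7-day half-life assumed for scheduling (section 3) as one-compartment accumulation gives a Day 14 multiple of 7.96. Then 200 mg daily looks like a 1591 mg single dose, Day 7 is only 67% of Day 14 for all exposure, and Cohort 3 alone exceeds the 800 mg single dose. The protocol's own predictions do not support that. Only M3 accumulates about 10-fold; the parent figure is about 646 mg, below 800, and the sum is about 872 mg, a marginal excess. Section 1.5 also describes disposition in animals as multiexponential, so a terminal half-life applied to one compartment can overstate accumulation.

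**Conclusion.** The point holds as a low-cost improvement to consider. On the schedule as written, Day 7 is the only planned draw on which rule d can spare more than the last dose, and Part 2 has fewer panels over two weeks of daily dosing than the single-dose parts have after one dose.

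The size is modest: about 1-3 percentage points at assumed event rates of 5-10%, less if both cases must share a parameter, and 2-3 doses spared if confirmation takes 2-3 days. The larger gains at 20-30% rest on rates that nothing in the documents supports. Exposure does rise after Day 7, but by how much is uncertain. On the protocol's predictions, Day 7 is a good sentinel for parent and a weaker one for M3.

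A reader might also infer that rule d cannot work or that subjects are unmonitored. Neither follows, since Day 7, Grade 2 follow-up and for-cause draws all remain. The figures rest on assumed event rates and onset pattern, dose linearity without a food effect, an unstated turnaround and a common start day within a cohort.

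**What to change.** For any Part 2 cohort not yet dosed (Cohort 3 or an added cohort), add one serum chemistry panel (ALT, AST, ALP, amylase, lipase and CPK) to the Day 10 predose trough draw. Specify an expedited repeat, so that a confirmed result is in hand within 2-3 days. Mark the panel in Table 16 and update Table 9: in-study clinical labs from 9 to 10 samples, 76.5 to at most 85.0 mL, total at most 331.1 mL. The sponsor and investigator can adjust the exact day.

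The cost is one panel and at most 8.5 mL per subject. No new visit or venepuncture is needed, because subjects are confined and a trough sample is already drawn that day. Section 3 allows the schedule to be revised, and the extra Part 2 ECG extractions were first introduced by clarification letter. The downside is a 0.4-6.4% chance of a false alarm before confirmation, under the assumed background rates. If all Part 2 cohorts have been dosed, make no change.
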